31. Administration, U.S.F.D. What is a Serious Adverse Event? [Internet]. 2016 [cited 2019 26 Oct]. Available from: <https://www.fda.gov/safety/medwatch/howtoreport/ucm053087.html>

ANTICIPATED OUTLINE

[figure not shown]

Figure 1: CONSORT Flow Diagram of participants through the trial. Control comparator group (a minimal home-based program); Intervention group (individualised treatment).

THE FIGURE BELOW IS DEPICTED WITH ANTICIPATED CHANGES FROM BASELINE TO 12 WEEKS FOLLOW-UP!

[figure not shown]

Figure 2: Trajectory in SPADI-score in the *Control comparator group* (*a minimal home-based program*) and *Intervention group* (*individualised treatment*) at baseline, 4-, 8-, and 12 (primary end-point) weeks after initiating the treatment. Values are mean (95% CI).

Table 1. Baseline characteristics in the ITT population*

	Intervention Group (N =XX)	Control Comparator Group (N =XX)	Total Combined (N =XX)
General characteristics			
Mean age — years			
Height — cm			
Weight — kg			
Body Mass Index — kg/m ²			
Smoking Habits:			
Smoker— no. (%)			
Current smoker— no. (%)			
Not a smoker— no. (%)			
Highest Education level:			
Short — no. (%)			
Medium — no. (%)			
Long — no. (%)			
Employment:			
Employed for wages — no. (%)			
Self-employed — no. (%)			
Sick leave — no. (%)			
Retired — no. (%)			
Other — no. (%)			
Index shoulder:			
Right side — no. (%)			
Left side — no. (%)			
Dominant side affected:			
Right side — no. (%)			
Left side — no. (%)			
Duration of shoulder symptoms — years			
Outcome measures			
SPADI score† — 0 to 100			
Shoulder pain — 0 to 10			
Shoulder function — 0 to 10			
GPE impression of the treatment's success — 0 to 7			
A-ROM in the affected shoulder — degree			
P-ROM in the affected shoulder — degree			
NRS maximum shoulder pain intensity — 0 to 10			
NRS shoulder pain during general activities — 0 to 10			
NRS shoulder pain at rest — 0 to 10			
NRS shoulder pain during sleep — 0 to 10			
NRS shoulder pain assessment during flexion/rotation/abduction — 0 to 10			

* Plus-minus values are mean \pm SD unless otherwise indicated

† The Shoulder Pain and Disability Index (SPADI) ranges from 0 (best) to 100 (worst), with lower scores indicating better disease status.

Table 2: Primary and Key Secondary Outcomes at 12 weeks in the ITT population*

Outcome	12 weeks after initiating the treatment		Between-Group Difference in Mean Improvement	
	Intervention Group	Control Comparator Group	Difference in LSMeans (95%CI)	P-Value
	Mean	SE	Mean	SE
Primary endpoint				
Change SPADI score — 0 to 100				
Key secondary outcome measures				
Change SPADI pain (0-10)				
Change SPADI function (0-10)				
Change Clinical response (SPADI change score)				
GPE impression of the treatment success (0-7)				
Change A-ROM in the affected shoulder (degree)				
Change P-ROM in the affected shoulder (degree)				
Number of treatments received due to shoulder symptoms (mean)				
NRS maximum shoulder pain intensity (0-10)				
NRS shoulder pain during general activities (0-10)				
NRS shoulder pain at rest (0-10)				
NRS shoulder pain during sleep (0-10)				
NRS shoulder pain assessment during flexion/rotation/abduction (0-10)				
Response to Treatment				
SPADI minimal important change criteria† no. (%)				

* All analyses will be based on the Intention-To-Treat (ITT) population: Using Repeated-Measures, Mixed Models (with no simple imputation for missing data); Estimates will be least squares means (LSMeans) and Standard Errors (SE) with the difference between groups reported with 95% Confidence Intervals (CI).

† Patients will be classified as having a clinically relevant change if the SPADI score improves by 8 points or more; missing data will be replaced by single-step non responder imputation.

Table 3: Serious Adverse Events at 12 weeks in the ITT population*

	Intervention Group	Control Comparator Group
Serious Adverse Event (SAE) - no (%)		
Musculoskeletal		
Deep infection, no. (%)		
Shoulder dislocation, no. (%)		
Shoulder fracture, no. (%)		
Cardiovascular		
Vascular injury (arterial and venous damage), no. (%)		
Pulmonary embolism, no. (%)		
Deep venous thrombosis, no. (%)		
Acute myocardial infarction, no. (%)		
Nervous system		
Nerve injury, no. (%)		
Deaths, no. (%)		
Discontinuation due to AE(s) — no. (%)		

* This table includes all Serious Adverse Events (SAE's) that occurred during the 12 weeks study period, but not necessarily a causal relationship with the treatment administered. An adverse event was classified as serious if it was fatal or life-threatening, required or prolonged inpatient hospitalisation, was disabling, resulted in (a congenital anomaly or birth defect), or required medical or surgical intervention to prevent permanent impairment or damage.

Appendix Table 1: Sensitivity Analysis at 12 weeks in the ITT population using a single step non-responder imputation*

Outcome	12 weeks after initiating the treatment		Between-Group Difference in Mean Improvement	P-Value		
	Intervention Group	Control Comparator Group				
Primary endpoint						
SPADI score — 0 to 100						
Key secondary outcome measures						
SPADI pain (0-10)						
SPADI function (0-10)						
Clinical response (SPADI change score)						
GPE impression of the treatment success (0-7)						
A-ROM in the affected shoulder (degree)						
P-ROM in the affected shoulder (degree)						
Number of treatments received due to shoulder symptoms (mean)						
NRS maximum shoulder pain intensity (0-10)						
NRS shoulder pain during general activities (0-10)						
NRS shoulder pain at rest (0-10)						
NRS shoulder pain during sleep (0-10)						
NRS shoulder pain assessment during flexion/rotation/abduction (0-10)						

* The primary outcome will be analysed using single step imputation, based on the data set where missing data is handled. All key secondary outcomes are analysed based on the Repeated-Measures, Mixed Models (based on all collected time points): Missing data will be replaced by simple single step imputation, where missing data is replaced by the value at baseline (baseline observation carried forward).

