Objectives: The primary efficacy objective is to compare the effect of the individualised treatment plan, relative to a minimal physiotherapeutic rehabilitation program, on changes in Shoulder Pain and Disability Index (SPADI) from baseline to 12 weeks after initiating the treatment, in women with late-term shoulder impairments after primary breast cancer surgery.

Methods: The study was designed as a randomised trial with a two-group comparison testing superiority hypothesis related to the primary and key secondary objectives. In total, 130 participants would randomised (allocation 1:1) to either an expert assessment of shoulder impairments followed by an individualised treatment plan or to follow a minimal physiotherapeutic rehabilitation program delivered in a pamphlet. The primary analysis will be based on the Intention to Treat (ITT) population; the ITT principle asserts the effect of a treatment policy (that is, the planned treatment regimen), rather than the actual treatment given (i.e., it is independent of treatment adherence). The analyses of the key secondary outcomes will be performed in a prioritized order. The analyses of the confirmatory secondary outcomes will be performed in sequence until one of the analyses fails to show the statistically significant difference, or until all analyses have been completed at a two-sided statistical significance level of 0.05. The continuous outcomes will be analysed based on Repeated-Measures Mixed Effects Models (time: 0, 4, 8, and 12 weeks from baseline).

Registration: ClinicalTrials.gov, identifier: NCT05277909. Registered on 11 March 2022.

INTRODUCTION

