The overview of the trial time-points of each outcome assessment is presented in the **Table 1** in the study protocol at the TRIALS journal (<https://doi.org/10.1186/s13063-022-06659-1>): “*Effectiveness of an expert assessment and individualised treatment compared with a minimal home-based exercise program in women with late-term shoulder impairments after primary breast cancer: Study protocol for a randomised controlled trial*”. The intervention start date (*Intervention group* or *Control comparator group*) for each patient is used to calculate the 4-, 8-, and 12-weeks follow-up time points.

STATISTICAL PRINCIPLES

Confidence intervals and p-values

All 95% confidence intervals (95% CIs), and *P-values* will be two sided. Adjustments for multiplicity will not be applied, but rather the analyses of the key secondary outcomes will be performed and interpreted in a prioritized order. The analyses of the confirmatory secondary outcomes will be performed in sequence until one of the analyses fails to show the statistically significant difference, or until all analyses have been completed at a statistical significance level of 0.05. The key secondary statistical tests will be reported with *P* values for hypothesis tests and claims of statistical significance.

Analysis populations

The primary analyses will be based on the Intention to Treat (ITT) population, i.e., based on the Full Analysis Set (having the outcome of interest measured at baseline). The ITT principle asserts the effect of a treatment policy (that is, the planned treatment regimen), rather than the actual

treatment given (i.e., it is independent of treatment adherence). Accordingly, participants allocated to a treatment group will be followed up, assessed and analysed as members of that group, irrespective of their adherence to the planned course of treatment (i.e., independent of withdrawals and cross-over phenomena) (8).

TRIAL POPULATION

Screening data

The total number of patients, screened for eligibility, will be collected, and presented in a CONSORT Flow Diagram ([Figure 1](#)) for documenting the flow of participants through the trial. The number of ineligible patients randomised by mistake, if any, will be reported including reason for ineligibility.

Eligibility criteria

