A key secondary outcome will be the between-group difference in change in a separate SPADI-pain-subscale ($\Delta\text{SPADIpain}_{12} = \text{SPADIpain}_{12\text{-weeks follow-up}} - \text{SPADIpain}_{\text{baseline}}$) from baseline to 12 weeks after initiating the treatment. SPADI is considered a valid and reliable

patient-reported questionnaire consisting of 5-item pain subscale are scored on a numeric rating scale that ranges from 0 (no pain) to 10 (worst pain) (9,14).

- *SPADI function [Time Frame: 0, 4, 8 and 12 weeks]*

A key secondary outcome will be the between-group difference in change in a separate SPADI-function-subscale ($\Delta\text{SPADI}_{\text{funcion}}_{12} = \text{SPADI}_{\text{funcion}}_{12\text{-weeks follow-up}} - \text{SPADI}_{\text{funcion}}_{\text{baseline}}$) from baseline to 12 weeks after initiating the treatment. SPADI is a valid and reliable patient-reported questionnaire consisting of 6-item pain subscale (exclusion of question three and seven) are scored on a numeric rating scale that ranges from 0 (no difficulty) to 10 (so difficult that required help) (9,14).

- *SPADI clinical response [Time Frame: 12 weeks (follow-up)]*

Response to treatment will be computed for the SPADI change score for each woman in both treatment groups and presented dichotomised (i.e. responder and non-responder) as number (and percentages) responders. Women will be classified as a responder if the SPADI change score improves by 8 points or more (\geq), corresponding to the minimal clinically important difference on SPADI (6,7) from baseline to 12 weeks follow-up.

- *Global perceived effect (GPE) [Time Frame: 4, 8 and 12 weeks]*

A key secondary outcome will be the between-group difference in GPE score 12 weeks after initiating the treatment.

The GPE will evaluate the impression of the treatment's success including overall shoulder problems on a 7-point Likert scale ranging from “markedly worse” to “markedly improved” (15,16).

- *Active Range of Motion (A-ROM) [Time Frame: 0 and 12 weeks]*

A key secondary outcome will be the between-group difference in change in A-ROM degrees ($\Delta\text{A-ROM}_{12} = \text{A-ROM}_{12\text{-weeks follow-up}} - \text{A-ROM}_{\text{baseline}}$) from baseline to 12 weeks after initiating the treatment. The smartphone inclinometer (GetMyROM) is considered valid and reliable to assess A-ROM in flexion, internal rotation, external rotation and abduction (17-21).

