- *Passive Range of Motion (P-ROM) [Time Frame: 0 and 12 weeks]*

A key secondary outcome will be the between-group difference in change in P-ROM degrees ($\Delta P-ROM_{12} = P-ROM_{12\text{-weeks follow-up}} - P-ROM_{\text{baseline}}$) from baseline to 12 weeks after initiating the treatment. The smartphone inclinometer (GetMyROM) is considered valid and reliable to assess A-ROM in flexion, internal rotation, external rotation and abduction (17-21).

- *Number of treatments received due to shoulder symptoms [Time Frame: 12 weeks (follow-up)]*

A key secondary outcome will be the between-group difference in mean number of treatments received due to shoulder symptoms from baseline to 12 weeks after initiating the treatment.

- *Maximum shoulder pain intensity [Time Frame: 0, 4, 8 and 12 weeks]*

A key secondary outcome will be the between-group difference in change in maximum pain intensity ($\Delta MaxPain_{12} = MaxPain_{12\text{-weeks follow-up}} - MaxPain_{\text{baseline}}$) from baseline to 12 weeks after initiating the treatment. The Numeric Rating Scale (NRS) is considered a valid, reliable and responsible single 11-item patient-reported pain scale that ranges from 0 (no pain) to 10 (worst pain) (22).

- *Shoulder pain during general activities [Time Frame: 0, 4, 8 and 12 weeks]*

A key secondary outcome will be the between-group difference in change in shoulder pain during general activities ($\Delta General\ activity\ pain_{12} = General\ activity\ pain_{12\text{-weeks follow-up}} - General\ activity\ pain_{\text{baseline}}$) from baseline to 12 weeks after initiating the treatment. The NRS is considered a valid, reliable and responsible single 11-item patient-reported pain scale that ranges from 0 (no pain) to 10 (worst pain) (22).

- *Shoulder pain at rest [Time Frame: 0, 4, 8 and 12 weeks]*

A key secondary outcome will be the between-group difference in change in shoulder pain at rest ($\Delta Pain\ at\ rest_{12} = Pain\ at\ rest_{12\text{-weeks follow-up}} - Pain\ at\ rest_{\text{baseline}}$) from baseline to 12 weeks after initiating the treatment. The NRS is considered a valid, reliable and responsible single

11-item patient-reported pain scale that ranges from 0 (no pain) to 10 (worst pain) (22).

- *Shoulder pain during sleep [Time Frame: 0, 4, 8 and 12 weeks]*

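### Baseline carry-forward is undefined for GPE and number of treatments, and for SPADI it is a single zero-change scenario that cannot by itself show robustness

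*SAP*

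**What the plan says.** **The imputation rule.** The Appendix Table 1 footnote (SAP) covers all key secondary outcomes and exempts none: "Missing data will be replaced by simple single step imputation, where missing data is replaced by the value at baseline (baseline observation carried forward". The table has rows for GPE and for number of treatments.

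**The schedules.** Under Key secondary outcomes, GPE is listed as "Global perceived effect (GPE) [Time Frame: 4, 8 and 12 weeks", without week 0. Number of treatments is listed as "Number of treatments received due to shoulder symptoms [Time Frame: 12 weeks (follow-up" and defined as the "between-group difference in mean number of treatments received due to shoulder symptoms from baseline to 12 weeks after initiating the treatment".

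**Related wording.**
- The Table 1 shell for baseline characteristics contains the row "GPE impression of the treatment's success — 0 to 7". It has no row for number of treatments.
- Analysis populations describes the primary analyses as "based on the Full Analysis Set (having the outcome of interest measured at baseline". The Table 2 footnote adds: "All analyses will be based on the Intention-To-Treat (ITT) population".
- The abstract says: "The continuous outcomes will be analysed based on Repeated-Measures Mixed Effects Models (time: 0, 4, 8, and 12 weeks from baseline".

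**SPADI.** Under Missing data and sensitivity analyses, the main analysis assumes Missing at Random. The third strategy replaces missing values with the baseline value, to be informative if data are Missing Not At Random. The section ends by judging robustness on whether the sensitivity analyses give similar results. The Appendix Table 1 sentence on the primary outcome does not name the replacement value, so for SPADI the rule comes from this third strategy.

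**The concern.** There are two linked problems.

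1. A rule that copies the baseline value forward needs a baseline value. A rating of how well treatment worked cannot exist before treatment, and a count that starts at baseline has no scheduled baseline measurement. A programmer could not produce these two rows without inventing a rule after seeing the data. The GPE row in Table 1 makes this worse, because it suggests that a baseline GPE exists to be carried.

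2. For SPADI the rule can be applied but tests little. It assigns zero change to every dropout in both arms. Whether this pulls the difference down or pushes it up depends on dropout and improvement in each arm. It does not examine dropouts who fare differently by arm, which is the main worry in an open comparison of individualised care with a pamphlet. If the main and carry-forward results agree, the report could claim robustness that has not been tested.

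**Working it through.** The plan has no figure of its own on this point to reproduce: the footnote states none, and the SAP gives no dropout rate and no expected improvement by arm. All rates and improvements below are assumptions. The yardsticks are the SAP's own: 8 SPADI points as the minimal relevant difference (Sample size and power considerations), and 4 points as the limit for absence of a clinically meaningful difference (Analysis methods).

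**Step 1. Is there a value to carry forward?**

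| Outcome | Scheduled weeks | Baseline value | Rule defined? |
|---|---|---|---|
| SPADI | 0, 4, 8, 12 | yes | yes |
| GPE | 4, 8, 12 | none | no |
| Number of treatments | 12 (count since baseline) | none | no |

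SPADI responder status is also a week-12 outcome, but it has its own rule (missing counts as non-response). If someone supplied a zero as the baseline count of treatments, an arm with true mean m and missing fraction p would show (1 − p)·m. That understates the count for anyone treated and then lost.

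**Step 2. Which SPADI analyses depart from Missing at Random?** The per-protocol analysis (Appendix Table 2) uses the mixed model without imputation. The as-treated analysis (Appendix Table 3) uses the mixed model on regrouped participants. Both change who is compared, not what is assumed about missing values. Non-responder imputation for the responder outcome repeats the no-improvement assumption. Carry-forward is therefore the only departure.

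**Step 3. Direction of the SPADI shift.** Count improvement as positive. Let p be the dropout fraction, μ the completers' improvement and d the dropouts' improvement, with I for intervention and C for control.

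- Carry-forward difference = (1 − pI)·μI − (1 − pC)·μC
- True difference = (1 − pI)·μI + pI·dI − [(1 − pC)·μC + pC·dC]
- Carry-forward minus truth = pC·dC − pI·dI

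No true difference, μ = 15 in both arms, dropouts like completers:
- pI = 0.10, pC = 0.25: 13.5 − 11.25 = **+2.25**
- rates swapped: 11.25 − 13.5 = **−2.25**
- equal rates: 0
- at 10%/25%, with μ from 8 to 20: 0.15 × 8 = 1.2 to 0.15 × 20 = 3.0
- at 10%/25%, with dropouts achieving half the completers' 15 points: 0.15 × 7.5 = 1.125; achieving none: 0

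Simulation with a baseline-adjusted linear model (SD of change 15.41 as in the SAP, assumed baseline/follow-up correlation 0.5) gave 2.2 to 2.3 at both 65 and 16 per arm for 10%/25%, and about 0 with equal dropout. The shift therefore does not depend on sample size or on using raw change scores.

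True difference 8 (16 versus 8), dropouts like completers, intervention rate first:
- 20%/10%: 12.8 − 7.2 = 5.6
- 10%/20%: 14.4 − 6.4 = 8.0
- 5%/20%: 15.2 − 6.4 = 8.8

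The last result is larger than the truth, so carry-forward is not always conservative.

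**Step 4. Dropouts who differ by arm.** Take completers at 18 versus 10 and 20% dropout in each arm. Carry-forward gives 0.8 × 18 − 0.8 × 10 = 6.4. If intervention dropouts do not improve and control dropouts improve like completers, the truth is 14.4 − 10 = 4.4. In the reverse case it is 18 − 8 = 10.0. The main analysis gives 8.0 if dropouts supply no week 4 or week 8 data.

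**The case against.** **The SPADI part is a preference.** The SAP names a main assumption and one departure from it, and says only that the departure is informative. That is not false. The shifts needed to overturn a clear result can also be large. With 65 per arm and an observed difference of 8, SE = 15.41 × √(2/65) = 2.70 and 8 − 1.96 × 2.70 = 2.70. Significance is lost at a shift, in the intervention arm only, of 2.70/0.05 = 54, 2.70/0.10 = 27 or 2.70/0.20 = 13.5 points for 5%, 10% or 20% missing. This stands as a reason for proportion: with little dropout the conclusion may be safe. But it takes a delta calculation to show that, and carry-forward does not supply one. The SAP also goes further than calling the analysis informative, since it judges robustness on similar results.

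**The main analysis uses weeks 4 and 8.** This is correct. A non-improving dropout seen at those visits pulls the estimate down. In a rough simulation (assumed linear improvement, random intercept, 20–25% dropout) the 8.0 in Step 4 fell to as low as about 6.7. The gap narrows, but the true 4.4 still lies below both planned results.

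**Stronger readings that the text does not support.**
- A reader might infer that the plan imputes zero treatments. The SAP never states, stores or carries a zero; the rule is simply undefined.
- A reader might infer that the analysis-set wording removes everyone from these two outcomes. That is strained: the same section says participants are analysed as randomised, and the fourth missing-data strategy accounts for all randomised participants. The wording does not fit these outcomes, and that is all.
- The abstract's week 0 is a summary. Analysis methods ties the four week levels to SPADI, and the Appendix Table 1 footnote refers to the time points collected.

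**Conclusion.** The point holds in two parts and should be corrected.

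**Certain, from the text alone.** The carry-forward rule has no source value for GPE or number of treatments, so two rows of Appendix Table 1 cannot be produced as written. The GPE row in Table 1 contradicts the GPE schedule, and the baseline requirement in the analysis-set wording does not suit either outcome. The week-12 contrasts for both outcomes are stated, so what needs correcting is the rules, not what is estimated.

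**Conditional on assumptions.** For SPADI, carry-forward is one fixed scenario that can favour either arm. With 15-point improvement in both arms, dropouts like completers and 10% versus 25% dropout, the spurious difference is 2.25 points either way (1.2 to 3.0 for improvements of 8 to 20). That is 2.25/8 = 28% of the minimal relevant difference and 2.25/4 = 56% of the 4-point limit. It is zero if dropouts truly do not improve, or if both dropout and the dropouts' improvement are equal across arms. Agreement between the main and carry-forward results is therefore not enough to claim robustness.

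A reader might take this to undermine the confirmatory SPADI test. It does not: that test rests on the mixed model under Missing at Random, which is unchanged.

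**What to change.** 1. In Appendix Table 1, take GPE and number of treatments out of the carry-forward rule, or state a non-baseline imputation value for each.
2. Analyse GPE at weeks 4, 8 and 12 without a baseline covariate, and number of treatments as a single week-12 count without baseline or repeated-measures terms.
3. Remove the GPE row from the Table 1 baseline shell.
4. In Analysis populations, do not require a baseline value for these two outcomes.
5. For SPADI, add multiple imputation with delta shifts varied separately by arm, reported as a tipping-point analysis. Keep carry-forward as one scenario, and base the robustness statement on the range of shifts.

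The cost is SAP wording and a modest amount of extra programming. No new data are needed.

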outcome, a 95% CI excluding differences greater than 4 SPADI points between groups will be interpreted as indicating absence of a clinically meaningful difference. Dichotomous outcome variables will be analysed with logistic regression, with identical fixed effect factors and covariates as the mixed linear model described above. Missing data for dichotomous outcomes will be computed based on conservative (non-responder) imputations.

Subgroup analyses (24) will be used to examine whether the observed overall treatment effect varies across participants subgroups, and to whether the effect is modified by the value of a variable assessed at baseline, analysed by the following thresholds: median age, median duration of shoulder symptoms, obesity ($BMI \geq 30 \text{ kg/m}^2$), dominant side affected (left vs right). This statistical approach to evaluate potential effect modifiers, will be a test for statistical interaction whether the treatment effect (net benefit on change in the SPADI score) varies across levels of the effect modifier (25).

Missing data and sensitivity analyses

To handle missing data, repeated-measures linear mixed effects models will be used (26-29). These models are considered valid if data are “*Missing at Random*” (i.e., any systematic difference between the missing values and the observed values can be explained by differences in observed data) (30).

The following four strategies for handling and interpretation of missing data will be applied in the sensitivity analysis:

1. We will attempt to follow up all randomised participants, even if they withdraw from allocated treatment (i.e., contact all individuals unless they explicitly stated that they had withdrawn their consent);
2. Perform a main analysis of all observed data that are valid under a plausible assumption about the missing data (i.e., data as randomised; using linear mixed effects models, assuming that data are “*Missing at Random*”);
3. Perform sensitivity analyses to explore the effect of departures from the assumption made in the main analysis (i.e., non-responder-imputation: using the value at baseline to replace missing data);

these models will be informative about the robustness in case data are “*Missing Not At Random*”); and

4. Account for all randomised participants, at least in the sensitivity analyses (including strategy 2 and 3, plus the corresponding analyses based on the per protocol population) (28).

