Thus, the following sensitivity analyses will be performed on various population analyses, including a non-responder imputation and per-protocol, to examine the robustness by revealed similar results in these sensitivity analyses. Robustness is a concept that refers to the sensitivity of the overall conclusions to various limitations of the data, assumptions, and analytic approaches to data analysis. Robustness implies that the treatment effect and primary conclusions of the trial are not substantially affected when analyses are carried out based on alternative assumptions or analytic approaches.

Additional analyse

No additional analyses on the primary and key secondary outcomes are planned from baseline to 12 weeks follow-up.

Harms

Serious adverse events (SAE) will be categorised in accordance with the definitions established by the United States Food and Drug Administration (e.g. hospitalisation or death) (31). All categorical types of SAE's will be presented for each group and statistical tested by using logistic regression. The SAEs will be presented as illustrated in **Table 3**.

Statistical software

All data analysis will follow the statistical methods described above, and will be performed applying STATA (Statacorp, College Station, Texas, USA) and SAS (SAS Institute Inc., Cary, North Carolina, USA) software.

REFERENCES

1. American Cancer Society. Breast Cancer Facts & Figures 2019-2020 [Internet]. 2020 [cited 2022 Aug 08, pp. 4]. Available from: <https://www.cancer.org/content/dam/cancer-org/research/cancer-facts-and-statistics/breast-cancer-facts-and-figures/breast-cancer-facts-and-figures-2019-2020.pdf>
3. World Medical Association (WMA). WMA Declaration of Helsinki – Ethical Principles for Medical Research Involving Human Subjects [Internet]. 1964 [cited 2018 Aug 14]. Available from: <https://www.wma.net/policies-post/wma-declaration-of-helsinki-ethical-principles-for-medical-research-involving-human-subjects>

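### For the dichotomous SPADI response, the non-responder sensitivity analysis in Appendix Table 1 repeats the main imputation, so the missing-responder assumption is not varied within the ITT population

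*SAP*

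**What the plan says.** The definition is in the SAP under Key secondary outcomes: "Women will be classified as a responder if the SPADI change score improves by 8 points or more", from baseline to the 12-week follow-up.

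Two places fix the main-analysis rule for missing responses. Analysis methods says: "Missing data for dichotomous outcomes will be computed based on conservative (non-responder) imputations". The dagger footnote of Table 2 says of the responder row that "missing data will be replaced by single-step non responder imputation". The model is also given in Analysis methods: "Dichotomous outcome variables will be analysed with logistic regression, with identical fixed effect factors and covariates as the mixed linear model described above".

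The sensitivity analysis is strategy 3 under Missing data and sensitivity analyses. Its stated purpose is to explore departures from the main analysis assumption, and it is described as "non-responder-imputation: using the value at baseline to replace missing data". Appendix Table 1 carries this out in the ITT population, lists clinical response as a row, and says in its footnote: "Missing data will be replaced by simple single step imputation, where missing data is replaced by the value at baseline (baseline observation carried forward". The same section presents the sensitivity analyses as a way "to examine the robustness by revealed similar results in these sensitivity analyses".

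**The concern.** A sensitivity analysis for missing data is informative only if it treats the missing women differently from the main analysis. For the continuous outcomes the plan does this: the main mixed model assumes Missing at Random, and baseline carried forward departs from that. For the responder outcome the main analysis already uses non-responder imputation, and the sensitivity analysis appears to apply the same rule under another name.

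Clinical response is third in the list of key secondary outcomes, which are tested in a prioritised sequence, and a responder proportion is easily quoted to clinicians. If the two results are printed in separate tables and found to agree, a reader may conclude that the result withstands different treatment of missing data, although nothing about that treatment was changed.

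**Working it through.** **Inputs from the SAP.** Threshold: improvement of 8 points (Key secondary outcomes). Main rule: missing counts as non-response (Analysis methods; Table 2 dagger footnote). Sensitivity rule: missing takes the baseline value (strategy 3; Appendix Table 1 footnote). A baseline value is always present, because the Full Analysis Set requires the outcome at baseline (Analysis populations). The SAP gives no expected response or loss rate, so there is no planned figure for this outcome to reproduce. The planned 65 per arm (Sample size and power considerations) serves below only as a denominator.

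**Step 1: status of each woman.** Improvement = SPADI at baseline − SPADI at week 12.

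- Week 12 observed: the same status in both analyses.
- Week 12 missing, main analysis: non-responder by rule.
- Week 12 missing, Appendix Table 1: week-12 value = baseline value, so improvement = 0. Since 0 < 8, non-responder.

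The two imputed data sets are identical. Under the same logistic regression, the odds ratio, confidence interval and p-value must be identical too.

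**Step 2: check by simulation.** Both rules were applied to the same simulated data: 65 or 16 women per arm, 5% to 30% missing, 2,000 data sets per setting. Mean improvements of 5 and 13 points and the loss rates are assumptions; the SD of change is the SAP's 15.41. Status mismatches: 0 in every setting. The complete-case risk difference, by contrast, departed from the main result by a mean absolute 0.018 (5% missing) to 0.065 (30% missing) at 65 per arm, and by 0.031 to 0.100 at 16 per arm.

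**Step 3: what a different rule could show.** Assume 65 per arm and about 55% against 35% responders among those observed, rounded to whole women. Entries are risk differences, intervention minus control. The bounds count all missing women as non-responders in one arm and responders in the other.

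| Missing (intervention / control) | Observed responders | Main | Appendix Table 1 | Complete case | Extreme bounds |
|---|---|---|---|---|---|
| 5 / 5 | 33/60, 21/60 | 12/65 = 0.185 | 0.185 | 12/60 = 0.200 | 7/65 = 0.108 to 17/65 = 0.262 |
| 10 / 10 | 30/55, 19/55 | 11/65 = 0.169 | 0.169 | 11/55 = 0.200 | 1/65 = 0.015 to 21/65 = 0.323 |
| 15 / 5 | 28/50, 21/60 | 7/65 = 0.108 | 0.108 | 0.560 − 0.350 = 0.210 | 2/65 = 0.031 to 22/65 = 0.338 |
| 5 / 15 | 33/60, 18/50 | 15/65 = 0.231 | 0.231 | 0.550 − 0.360 = 0.190 | 0/65 = 0 to 20/65 = 0.308 |

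For 10 missing per arm the odds ratio is (30 × 46)/(19 × 35) = 2.08 under both planned rules and (30 × 36)/(19 × 25) = 2.27 among completers. In the last row non-responder imputation enlarges the difference, so the conservative label does not hold for every pattern of loss.

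**Step 4: the other planned tables.** Appendix Table 2 lists clinical response in the per-protocol population without imputation, so it changes population and missing-data rule together. Appendix Table 3 lists it in four as-treated groups, so it changes the comparison. Neither varies the missing-responder assumption while keeping the ITT population.

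**The case against.** Four counter-arguments deserve an answer.

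*The tables do not plainly say the same thing.* Table 2 has two responder rows. One carries the dagger and non-responder imputation. The other, a clinical-response change row among the key secondary outcomes, has no dagger and falls under a footnote of mixed models without simple imputation. Appendix Table 1 repeats the undaggered label, and its footnote says: "All key secondary outcomes are analysed based on the Repeated-Measures, Mixed Models (based on all collected time points". Read literally, main and sensitivity results could differ in model, and for the undaggered row in imputation as well. This stands as a conflict to be reconciled. It does not restore the check: the outcome is dichotomous and defined only at 12 weeks, and Analysis methods gives it logistic regression with non-responder imputation. Any difference produced by a model swap would not be evidence about missing data.

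*The outcome is examined elsewhere.* A reader might infer that its robustness is never tested. The SAP does not support that: the per-protocol and as-treated tables both list it and can give different results. What is absent is a change of missing-data assumption within the ITT population.

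*The robustness wording is about something else.* A reader might also infer that the SAP declares this row robust by construction. It does not. The section speaks of overall and primary conclusions, and strategy 3 departs from the Missing at Random model of strategy 2. For primary SPADI that departure is genuine. The risk lies in how agreement in this one row would be read.

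*The imputation is conservative and the consequence small.* With equal loss it shrinks the difference, as intended, and no step of the testing sequence depends on a sensitivity result. Both are fair. The use of non-responder imputation as the main rule is not disputed; repeating it is simply not a check on it.

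**Conclusion.** The point holds in a limited form. For the dichotomous SPADI response, the Appendix Table 1 analysis is redundant: no woman's status can differ from the main ITT analysis, whatever the loss, so strategy 3's purpose is not met for this outcome. This follows from the definitions alone, on the reading that Analysis methods and the Table 2 dagger footnote govern the outcome.

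How much a real check would reveal depends on loss and response rates that the SAP does not give. Under the assumptions shown, the complete-case difference departs from the planned result by 0.015 (0.200 − 0.185) with 5 missing per arm and by about 0.10 (0.210 − 0.108) with 15 against 5 missing. One key secondary outcome is affected. The primary analysis, the main responder result and the testing sequence are unchanged.

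**What to change.** 1. In Appendix Table 1, replace the clinical-response row with an ITT analysis under a different assumption. Possible wording: *Week-12 SPADI is multiply imputed from treatment arm and SPADI at weeks 0, 4 and 8 (strata included only if numbers allow), dichotomised at an improvement of 8 points, analysed by the logistic regression specified under Analysis methods, and combined by Rubin's rules.* The sample-size correction reports only 31 participants from the Region of Southern Denmark. The Central Denmark Region is also eligible, so the total is unknown, but it may fall well short of 130. If it is too small for stable imputation, use best/worst-case or tipping-point bounds instead.
2. Add a footnote that single-step non-responder imputation is already the main analysis for this outcome.
3. Reconcile the undaggered clinical-response row of Table 2, and the mixed-model footnotes of Table 2 and Appendix Table 1, with the logistic regression and non-responder rule in Analysis methods.

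The cost is one extra analysis of SPADI data already collected at weeks 0, 4, 8 and 12, plus footnote edits.
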